When cabozantinib or pembrolizumab are discontinued for reasons deemed to be related to one or the other agent, the protocol calls for the discontinuation of both agents until and when the toxicities have reached a tolerable level (as specified in the dose modification sections) at which time both agents will be re-initiated. Patients who have interruption of both agents for more than 6 consequential weeks will be removed from the study; response assessment for these patients will still be assessed if available; in addition to assessment of OS and PFS based on the intent to treat analysis principle.	Assigned dose	First Dose Level Reduction
	40-mg cabozantinib oral qd	20-mg cabozantinib oral qd

Table 3-3: Dose Modifications of Cabozantinib for Treatment-Related AEs

CTCAE v.4.0 Grade	Recommended Guidelines for Management ^a
Grade 1 AEs	Add supportive care as indicated. Continue cabozantinib treatment at the current dose level if AE is manageable and tolerable.
Grade 2 AEs which are tolerable and are easily managed	Continue cabozantinib treatment at the current dose level with supportive care.
Grade 2 AEs which are intolerable and cannot be adequately managed	At the discretion of the investigator, cabozantinib should be dose reduced or interrupted. Note: It is recommended that dose holds be as brief as possible.
Grade 3 AEs (except clinically non-relevant laboratory abnormalities)	Cabozantinib should be interrupted unless the toxicity can be easily managed with a dose reduction and optimal medical care. Note: It is recommended that dose holds be as brief as possible.
Grade 4 AEs (except clinically non-relevant laboratory abnormalities)	Subjects should have cabozantinib interrupted immediately. Discontinue cabozantinib unless the following criteria are met: 
• Subject is deriving clear clinical benefit as determined by the investigator and agreed by the Sponsor• Toxicity can be managed with a dose reduction following recovery to Grade 1 (or baseline) and optimal medical care

AE, adverse event.

Note: The dose delay and modification criteria for specific medical conditions are provided in Section 3.3.2. For re-treatment criteria of study treatment after a dose hold see Section 3.3.1.1.

^a Study treatment dose adjustment is only needed if the toxicity was deemed related to cabozantinib treatment or had an unclear relationship to cabozantinib treatment.

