Hyperglycemia, severe (Grade 3); also administer antihyperglycemics.

Hyperthyroidism, severe (grade 3) or life threatening (grade 4); manage with thionamides and beta-blockers as appropriate.

Hypophysitis, grade 2 (symptomatic); also administer corticosteroids (followed by a taper) and hormone replacement therapy if appropriate.

Hypoparathyroidism (Low levels of parathyroid hormone) (may occur rarely (<1%) which may result in low blood calcium and cause muscle cramps or spasms; fatigue or weakness; numbness, tingling or burning in fingertips, toes or lips

Nephritis, grade 2; also administer corticosteroids (prednisone 1 to 2 mg/kg/day [or equivalent] followed by a taper).

Pneumonitis, moderate (grade 2); also administer corticosteroids (prednisone 1 to 2 mg/kg/day [or equivalent] followed by a taper).

Other treatment-related toxicity, severe or grade 3; may require corticosteroids (based on severity). Upon improvement to grade 0 or 1, initiate corticosteroid taper and continue to taper over at least 1 month. Restart pembrolizumab if the adverse reaction remains at grade 0 or 1 following corticosteroid taper. May consider other systemic immunosuppressants if not controlled by corticosteroids (based on limited data).

Withhold (may resume upon recovery to grade 0 or 1 toxicity) or discontinue for:

Hyperthyroidism, severe (grade 3) or life-threatening (grade 4); manage with thionamides and beta-blockers as appropriate.

Hypophysitis, severe (grade 3) or life-threatening (grade 4); also administer corticosteroids and hormone replacement as appropriate.

Permanently discontinue for:

Adverse reactions that are life-threatening, persistent grade 2 or 3 adverse reaction (excluding endocrinopathies controlled with hormone replacement therapy) that does not recover to grade 0 or 1 within 12 weeks after the last pembrolizumab dose, or any recurrent severe or grade 3 treatment-related adverse reaction. Also administer corticosteroids (may consider other systemic immunosuppressants if not controlled by corticosteroids [based on limited data]).

Colitis, life-threatening (grade 4); also administer corticosteroids (prednisone 1 to 2 mg/kg/day [or equivalent] followed by a taper).

Immune mediated adverse reactions: Discontinue permanently if unable to reduce corticosteroid dose to prednisone \leq 10 mg/day (or equivalent) within 12 weeks.

Infusion-related reaction, grade 3 or 4.

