17. SAFETY

- **Adverse Events and Laboratory Abnormalities**

- **Adverse Events**

An AE is any untoward medical occurrence in a patient or clinical investigation subject who has been enrolled in a clinical study and who may have been given an investigational product, regardless of whether or not the event is assessed as related to the study treatment. An AE can therefore be any unfavorable and unintended sign (including an abnormal laboratory finding), symptom, or disease temporally associated with the use of an investigational product, regardless of whether or not the event is assessed as related to the investigational product. Pre-existing medical conditions that worsen during a study should be recorded as AEs. Abnormal laboratory values, ECG findings, or vital signs are to be recorded as AEs if they meet the criteria described in Section 3.3.

All untoward events that occur after informed consent through 30 days after the decision to discontinue study treatment (or the date the subject is deemed to be a screen failure) are to be recorded by the investigational site. This requirement includes AEs from unscheduled as well as scheduled visits.

Assessment of the relationship of the AE to the study treatment by the investigator is based on the following two definitions:

- Not Related: A not-related AE is defined as an AE that is not associated with the study treatment and is attributable to another cause or there is no evidence to support a causal relationship;
- Related: A related AE is defined as an AE where a causal relationship between the event and the study treatment is a reasonable possibility. A reasonable causal relationship is meant to convey that there are facts (eg, evidence such as dechallenge/rechallenge) or other clinical arguments to suggest a causal relationship between the AE and study treatment.

- **Serious Adverse Events**

The SAE definition and reporting requirements are in accordance with the International Conference of Harmonisation (ICH) Guideline for Clinical Safety Data Management: Definitions and Standards for Expedited Reporting, Topic E2A.

An SAE is defined as any untoward medical occurrence that at any dose:

- Result in death;
- Is immediately life-threatening (ie, in the opinion of the investigator, the AE places the subject at immediate risk of death; it does not include a reaction that, had it occurred in a more severe form, might have caused death);

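### The Grade 3 toxicity rules for cabozantinib, for pembrolizumab and for both agents together are not reconciled, and the causality definition does not supply the per-agent attribution they need

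*Combined protocol and SAP*

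**What the plan says.** Three sets of rules in the combined protocol and SAP apply to a Grade 3 adverse event.

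- **Cabozantinib, Table 3-3 (Section 3.3), Grade 3 row:** "Cabozantinib should be interrupted unless the toxicity can be easily managed with a dose reduction and optimal medical care". Footnote a limits the trigger: "Study treatment dose adjustment is only needed if the toxicity was deemed related to cabozantinib treatment or had an unclear relationship to cabozantinib treatment".
- **Pembrolizumab, Section 3.4.1:** the list of reasons to withhold, with resumption allowed on recovery to grade 0 or 1, ends with a residual entry: "Other treatment-related toxicity, severe or grade 3; may require corticosteroids (based on severity". The list of reasons to discontinue permanently includes "any recurrent severe or grade 3 treatment-related adverse reaction".
- **Both agents, Section 3.3, text beside Table 3-2:** if either drug is stopped for a cause attributed to one of the two, "the protocol calls for the discontinuation of both agents until and when the toxicities have reached a tolerable level". The sentence ends by having both agents restarted at that time. The next sentence adds: "Patients who have interruption of both agents for more than 6 consequential weeks will be removed from the study".

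Causality is defined in Section 17: "Assessment of the relationship of the AE to the study treatment by the investigator is based on the following two definitions". The two categories are related and not related, each judged against the study treatment. Section 18 repeats this without naming an agent.

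**The concern.** Each rule can be followed on its own, but together they can give different instructions for one event. Restarting both agents cannot be squared with stopping one of them for good, and nothing says whether cabozantinib continues alone. The instruction also depends on which drug is held responsible, an attribution that the adverse event definition does not ask for.

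Two things are at stake. Two sites could treat the same event differently, so exposure to the combination, on which ORR and PFS are judged, would depend partly on how the text is read. Describing the toxicities of the regimen is also a secondary objective, and the definition in force does not require the attribution that this description would need.

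**Working it through.** No sample size, power or event count underlies this point, so there is no planned figure to reproduce. The check is a comparison of the texts, followed by one calculation for scale.

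**Step 1. Trigger and action of each rule**

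| Rule | Trigger | Action |
|---|---|---|
| Table 3-3, Grade 3 | Related or unclear relationship to cabozantinib | Interrupt cabozantinib, or reduce it with optimal medical care and no interruption |
| Section 3.4.1, residual entry | Treatment-related, agent not stated, Grade 3, no entry of its own | Withhold pembrolizumab |
| Section 3.4.1, recurrence | Treatment-related, agent not stated, recurrent Grade 3 | Stop pembrolizumab permanently |
| Section 3.3, both agents | Either drug discontinued for a reason tied to one of them | Stop both, then restart both when tolerable |

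The withhold entry is residual. Grade 3 nephritis, pneumonitis and infusion reactions are permanent stops at first occurrence, and Grade 3 hypophysitis is withhold or discontinue.

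**Step 2. Three cases, using Grade 3 fatigue**

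Section 3.3.2.5 refers fatigue to Table 3-3. It has no entry of its own in the Section 3.4.1 dosing lists, so it falls in the residual entry.

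- *First event, blamed on cabozantinib alone, easily managed by reduction and care.* Table 3-3 allows cabozantinib to continue at a lower dose. Neither drug is stopped, so the both-agents sentence is not triggered. If *treatment-related* in Section 3.4.1 means pembrolizumab-related, there is no conflict.
- *First event, blamed on both drugs or unclear.* Footnote a brings in Table 3-3, so reduction without interruption is open. If both drugs are blamed, Section 3.4.1 withholds pembrolizumab. If the cause is unclear, Section 3.4.1 does not say. If a hold counts as a discontinuation, the both-agents sentence then stops the cabozantinib that Table 3-3 would have continued.
- *Recurrent event, blamed on pembrolizumab.* Section 3.4.1 ends pembrolizumab. The both-agents sentence stops both and restarts both on recovery. These cannot both be followed, whichever meaning of *treatment-related* is taken.

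**Step 3. Attribution needed against attribution defined**

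Per-agent attribution is presupposed by footnote a, by the Section 3.3 text on interruption for cabozantinib-related events, by the both-agents sentence, by Section 3.3.2.8 on hypertension and by the replacement rule in Section 2.2.1. Sections 17 and 18 define or mention relation to the study treatment only.

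Usage elsewhere does not settle the term. Table 3-3 has *treatment-related* in its title, but its footnote means cabozantinib. The DLT definition in Section 2.2.1 applies the term in the setting of the combined regimen. In Section 2.7 the minimum dose of study treatment is 20 mg once daily, which can only mean cabozantinib.

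**Step 4. Scale**

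Fatigue, diarrhea and decreased appetite are listed for cabozantinib (Section 1.2.3.2.1) and for pembrolizumab (adverse reactions in Section 3.4.1). Take the pooled single-agent cabozantinib rates p at Grade 3 or above and n = 34 from Section 18. The expected count is 34 × p, and P(at least one) = 1 − (1 − p)^34.

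- Fatigue: 34 × 0.153 = 5.2; 1 − 0.847^34 = 0.996
- Diarrhea: 34 × 0.104 = 3.5; 1 − 0.896^34 = 0.976
- Decreased appetite: 34 × 0.056 = 1.9; 1 − 0.944^34 = 0.86

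These figures show only that such events are likely to occur in the trial. They do not count patients for whom the rules collide.

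**The case against.** The strongest reply is that Section 3.4.1 is single-drug text. It sits under a heading announcing drug information on pembrolizumab, and its Grade 3 entries go on to corticosteroids and a taper. *Treatment-related* there most naturally means related to pembrolizumab. That is fair. A reader might infer that a pure cabozantinib effect, such as recurrent Grade 3 hypertension, must end pembrolizumab. The documents do not support this, because it follows only if the term means the combination.

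Two further inferences also fail. One is that the both-agents sentence cancels dose reduction under Table 3-3. It is triggered when an agent is discontinued, and a reduction stops neither agent. For some toxicities the option is absent anyway: Table 3-4 interrupts treatment for Grade 3 PPES. The other is that the recorded data cannot show which drug was blamed. The case report form is not in the documents, so per-agent recording is unspecified, not shown to be missing.

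It can also be said that the both-agents sentence was meant for temporary holds, since it points to the dose modification sections for the tolerable level. That may be the intention, but the sentence makes no exception for permanent discontinuation. Finally, for patients removed after more than six weeks off both agents, Section 3.3 keeps available response assessments and analyzes PFS by intent to treat. The effect would therefore be on exposure and consistency, and no bias in ORR or PFS has been shown.

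Three things remain after these replies: the contradiction between restarting both agents and the permanent stop, the undefined term for events blamed on both drugs or of unclear cause, and a causality definition that does not ask for the agent.

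**Conclusion.** The point holds as one direct contradiction and two gaps. The contradiction, between restarting both agents in Section 3.3 and permanently stopping pembrolizumab in Section 3.4.1, needs no assumption about what *treatment-related* means. The first gap, that the term is undefined for the combination, is most serious for toxicities shared by the two drugs. The second gap is that Section 17 does not require the per-agent attribution on which the dosing rules depend.

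The number of patients affected cannot be derived. The permanent stop needs recurrence, and the documents give neither a recurrence rate nor a split of attribution between the drugs. The expected counts above assume that pooled, any-cause, single-agent rates carry over to this population and starting dose. They include Grade 4 and 5 events, so adding up such rates would not measure the conflict. The point should be corrected because it bears on patient safety and combination exposure. It does not invalidate the design.

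**What to change.** 1. In Section 3.3, reconcile the sentence that restarts both agents with the permanent-discontinuation list in Section 3.4.1 and with the Grade 3 row of Table 3-3. State what happens to the other drug, and cover events attributed to both drugs or of unclear cause.
2. In Section 3.4.1, state which agent *treatment-related* refers to in the Grade 3 and recurrent Grade 3 entries.
3. In Section 17, require causality to be recorded separately for cabozantinib and for pembrolizumab, and carry this into Section 18.

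Which clinical action applies in each case is for the sponsor to decide. The cost is wording in four sections and, if the form does not already have it, one extra causality field per adverse event.

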3.3.1.1 Cabozantinib Dose Reinstitution and Reescalation

If the subject recovers from his or her toxicities to CTCAE v.4.0 Grade ≤ 1 or to the baseline value (or lower) and the toxicity was unrelated to study treatment, then study treatment may be restarted with no change in dose.

If the subject recovers from his or her toxicities to Grade ≤ 1 or to the baseline value (or lower) the toxicity was deemed possibly related to study treatment, then study treatment may be restarted at a reduced dose (see Table 3-2 for the schedule of dose reductions).

Subjects receiving a daily dose of 20 mg may be restarted at the same dose if deemed safe at the discretion of the investigator. Subjects unable to tolerate a daily dose of 20 mg should discontinue study treatment.

Re-escalation to the previous dose, (but not higher than 40 mg/day) may be allowed at the discretion of the investigator and agreement of the Sponsor for AEs which have resolved or recovered to Grade 1 (or baseline value) and deemed tolerable and easily managed by optimized supportive treatment. Dose re-escalation is not allowed for a drug-related dose reduction triggered by Grade 4 hematologic toxicities or by Grade 4 AEs affecting major organs (eg, central nervous system, cardiac, hepatic, renal).

3.3.2 Warnings and Precautions and Guidelines for the Management of Adverse Events

The most frequent adverse events experienced by $\geq 20\%$ of subjects treated with cabozantinib were diarrhea, fatigue, nausea, decreased appetite, vomiting, weight decreased, PPES, constipation, hypertension, dysgeusia, dysphonia, and asthenia.

Adverse events associated with laboratory abnormalities experienced by $\geq 5\%$ of subjects treated with cabozantinib include anemia, AST increased, ALT increased, hypothyroidism, hypokalemia, hypomagnesemia, thrombocytopenia, hypocalcemia, hypophosphatemia, lipase increased, lactate dehydrogenase (LDH) increased, neutropenia, ALP increased, hyponatremia, and leukopenia. Mild to moderate QTc interval prolongation (10-15ms) has also been observed with a QT interval calculated by the Fridericia formula (QTcF) not exceeding 500 ms.

Subjects may also experience medically important but less frequent adverse events including arterial and venous thrombotic AEs (eg, DVT, pulmonary embolism [PE], transient ischemic attack [TIA], and myocardial infarction [MI]), severe hemorrhagic events, proteinuria, wound healing complications, GI perforation, abscesses including intra-abdominal and pelvic abscess,

GI and non-GI fistulae formation, osteonecrosis, and reversible posterior leukoencephalopathy syndrome (RPLS).

Cabozantinib treatment should be permanently discontinued for the following adverse events: visceral perforation or fistula formation, severe hemorrhage, serious arterial thromboembolic events, nephrotic syndrome, malignant hypertension, hypertensive emergency, persistent uncontrolled hypertension despite optimal medical management, osteonecrosis of the jaw (ONJ), and RPLS.

Guidelines for the management of AEs (ie, dose interruptions and dose reductions) are presented in the next sections. Each dose reduction of cabozantinib should be to one dose level lower than the current dose. Dose reductions of more than one dose level are acceptable per Investigator judgment. All AEs should also be managed with supportive care at the earliest signs of toxicity. Adverse reactions are presumed to be attributable to study drug. Adverse events classified as “not related” are defined as AEs that are, without question, not associated with the study treatment and definitely attributable to another cause.

The predicted effective plasma half-life of cabozantinib is 55 hours. Thus, when initiating therapy with cabozantinib, it will take most subjects 2 to 3 weeks to reach steady state. If AEs attributable to cabozantinib occur within the initial 3-week period of dosing, early intervention with dose modifications may be justified for AEs that, if worsened, could potentially be dangerous or debilitating, because without a dose adjustment, systemic exposure of cabozantinib might be expected to increase after the onset of the AE.

Events that generally have an early onset include hypocalcemia, hypokalemia, thrombocytopenia, hypertension, PPES, abdominal pain, mucosal inflammation, constipation, diarrhea and vomiting. In addition, earlier onset for events of dehydration was observed in subjects with CRPC when compared with subjects with other tumor types.

3.3.2.1 Guidelines for Management of Potential Adverse Events

Sections 3.3.2.2 – 3.3.2.19 present management guidelines or warnings/precautions for the following cabozantinib treatment-emergent adverse events/serious adverse events of particular interest.

- Gastrointestinal disorders (diarrhea, nausea and vomiting, dehydration [prostate cancer studies], stomatitis and mucositis)
- Hepatobiliary disorders (elevated ALT and AST)

- Hematological disorders
- Fatigue, anorexia, and weight loss
- Skin disorders (palmar-plantar erythrodysesthesia syndrome [PPES] and rash)
- Wound healing and surgery
- Hypertension
- Thromboembolic events (venous and arterial)
- Proteinuria
- QTc prolongation
- Hypophosphatemia
- Thyroid function disorders
- Hemorrhagic events
- Osteonecrosis of the jaw (ONJ)
- Angioedema
- Musculoskeletal and connective tissue disorders
- Respiratory, thoracic, and mediastinal disorders

Please refer to the Investigator's Brochure for additional practice guidelines and management recommendations for these and other AEs potentially related to cabozantinib treatment (e.g. intra-abdominal and pelvic abscess; nervous system disorders; infections and infestations; and respiratory thoracic and mediastinal disorders) use in specific populations, and overdose and first aid measures for accidental cabozantinib exposure.

As with all investigational products, unknown AEs may occur. Subjects should be monitored closely for all AEs. As with other agents in development, additional AEs are unknown.

3.3.2.2 Gastrointestinal Disorders

The most common non-hepatobiliary GI AEs reported in clinical studies with cabozantinib regardless of causality are diarrhea, nausea, decreased appetite, vomiting, constipation, stomatitis and abdominal pain.

Diarrhea

Subjects should be instructed to notify their physician immediately at the first signs of poorly formed or loose stool or an increased frequency of bowel movements. Administration of antidiarrheal/antimotility agents is recommended at the first sign of diarrhea as initial management. Some subjects may require concomitant treatment with more than one antidiarrheal

agent. When therapy with antidiarrheal agents does not control the diarrhea to tolerable levels, study treatment should be temporarily interrupted or dose reduced per Table 3-3.

In addition, general supportive measures should be implemented including hydration, correction of fluid and electrolyte abnormalities, small frequent meals, and stopping lactose-containing products, high fat meals, and alcohol.

Nausea and Vomiting

Antiemetic agents are recommended as clinically appropriate at the first sign of nausea and vomiting or as prophylaxis to prevent emesis, along with supportive care in accordance to clinical practice guidelines. The 5-HT3 receptor antagonists are recommended over chronic use of NK-1 receptor antagonists. When therapy with antiemetic agents does not control the nausea or vomiting to tolerable levels, study treatment should be temporarily interrupted or dose reduced per Table 3-3.

Dehydration may be associated with vomiting and monitoring for and correction of fluid and electrolyte disturbances should be implemented.

Stomatitis and Mucositis

Preventive measures may include a comprehensive oral examination to identify and treat any potential risk for complications before study treatment is initiated. Appropriate correction of local factors should be instituted as indicated, such as modification of ill-fitting dentures and appropriate care of gingivitis.

During treatment with cabozantinib good oral hygiene and standard local treatments such as nontraumatic cleansing and oral rinses (eg, with a weak solution of salt and baking soda) should be maintained. The oral cavity should be rinsed after meals, and dentures should be cleaned and brushed often to remove plaque. Local treatment should be instituted at the earliest onset of symptoms. Obtain bacterial/viral culture if oral infection is suspected and treat infection as indicated by local guidelines. When stomatitis interferes with adequate nutrition and local therapy is not adequately effective, dose reduction or temporary withholding of cabozantinib should be considered per Table 3-2 and Table 3-3.

